1.2 METHODS

Participants

All participants will be diagnosed as a stroke and will be recruited from the departments of the Neuromedical and Physical Medicine and Rehabilitation, Yangon General Hospital (YGH) and the National Rehabilitation Hospital (NRH) in Yangon, Myanmar. Eligible participants will be randomly allocated into either the experimental or control groups. For allocation of the participants, a computer-generated list of random number will be used. In order to maintain recruitment balance between groups throughout the trial, a permuted block randomization process will be used within each strata using block sizes of at least 2 with all blocks divisible by 2. The sequence generation and allocation concealment will be managed by the researcher. To prevent inadequate concealment of allocation sequence, properly randomizing method using sequentially numbered, opaque sealed envelopes (SNOSE) will be used in this study. The allocation envelope will be prepared by using the aluminum foil and carbon paper. The aluminum foil will be used to ensure opaque and the allocation sheet inside cannot read against the light. The carbon paper will be used to prevent violations of allocation concealment. The treatment allocation sheet of standardized-size paper will be fold to fit with envelop. Place 1 sheet of carbon paper on top of the folded allocation sheet with the carbon side facing the paper so that writing on the front of the envelop is transferred to the treatment allocation paper inside. Then place this carbon paper and allocation sheet together inside aluminum foil wrapper. Finally, place complete insert into the envelope properly (290). Group assignment will be communicated directly to the therapist for the implementation on a single participant basis. In this study, the assessments will be done by the researcher. The assessor and the participants will be blinded from the study.

Study Design

The study design will be a randomized double blind balanced parallel-group (1:1).

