1.3 SELECTION CRITERIA

Inclusion criteria

1. First stroke diagnosed by neurologists and has paresis on the unilateral side of the body
2. Age between 18 and 75 years
3. Poststroke duration between 3–12 months confirmed by CT report.
4. Patients with middle cerebral artery (MCA) involvement
5. Ability to walk at least 10 meters with or without using assistance (walking aid and/or orthosis).
6. Functional Ambulation Category (FAC) ≥ 3 from the total of 5 score
7. Good cognition assessing by the Mini Mental State Examination (MMSE) ≥ 24 from the total of 30 score
8. National Institutes of Health Stroke Scale (NIHSS) < 14 from the total of 42 score
9. Proper MI ability assessing by the Kinesthetic and Visual Imagery Questionnaire (KVIQ–10) ≥ 3 from the total of 5 score

Exclusion criteria

1. Unstable cardiopulmonary problems (resting heart rate > 120 bpm, resting systolic blood pressure > 180 mmHg and resting diastolic blood pressure > 100 mmHg)
2. Other neurological conditions such as Parkinson's disease, Alzheimer's disease, or epilepsy
3. Orthopedic and rheumatologic disorders with weight bearing pain
4. Unable to communicate or unable to follow commands
5. Serious cardiac conditions such as hospitalization for heart disease within 3 months, active angina, serious cardiac arrhythmias, hypertrophic cardiomyopathy, severe aortic stenosis
6. Patients with unilateral spatial neglect
7. Patients with ataxic movement
8. Patients under medications with muscle relaxing effect

Termination Criteria

1. Borg scale for Rating Perceived Exertion (RPE) > 13 from the total of 20 score
2. Drop in systolic blood pressure 10 mmHg (persistently below baseline), despite an increase in workload, when accompanied by any other evidence of ischemia
3. Central nervous system symptoms such as dizziness, or near syncope
4. Signs of poor perfusion such as cyanosis or pallor
5. Severe adverse event, this means falls or incidents leading to injury requiring hospital or general practitioner visit
6. Another episode of stroke

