1.5 PROCEDURE

All participants will be explained about details of the study and the interventions. After that, they will be asked to sign on the written consent approving by the committee of the institution prior to participate in study. All participants will be randomly allocated the participants into the experimental (SPCCT with MI) or the control (SPCCT with health education) groups. All participants will be screened following the criteria and will be collected the demographic data.

Both groups will receive the same program of SPCCT by physiotherapist who have 5 years experienced in neurological condition. Prior to training, tasks will be demonstrated using clear instructions. Seven lower extremity mobility tasks will be used in the SPCCT program. The tasks were selected from the study of Dean et al and adapted to be appropriate for improving gait function in patients with stroke. The trained tasks for the MI will be similar to the tasks in SPCCT to getting the transfer effects of training. The experimental group will receive MI training, whereas, the control group will receive health education which both will be provided by the researcher. Both groups will be matched for duration and frequency of the therapy sessions.

All outcome measures will be assessed by the therapist who have been trained the outcome measures of the study. As the primary outcome measurements, spatio-temporal variables will be measured by using two dimensional motion analysis method. The protocol of this method was proved to be valid and reliability from previous pilot study. For functional gait variables, six-minute walk test will be assessed for determining walking endurance, step test will be assessed for dynamic balance, and Timed Up and Go (TUG) test will be assessed for mobility function.

As the secondary outcome measure, the strength of hip flexor, hip extensor, knee flexor, knee extensor, ankle dorsiflexor, and ankle plantarflexor muscles will be assessed by using hand-held dynamometer. Muscle spasticity will be assessed by using the Modified Ashworth Scale (MAS). The outcome measures will be assessed at the baseline, after 2 weeks and 4 weeks intervention. For the safety, the therapist will measure blood pressure, pulse rate and fatigue level in the assessments, just before the training, and rest period during the training program.

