The participants will be trained to familiarize with the MI tasks. The participants will be explained about the procedures. During the training, they are not supposed to perform the activity but only imagine about the tasks. Video will be used together with the explanation to perform and demonstrate about the tasks performing. After this session, the participants will perform the tasks physically. Then, the participants will be trained with both visual and kinesthetic MI tasks. Imagine the movement using the first person perspective both for visual imagery and the kinesthetic imagery. For the visual imagery, the participants will be requested to visualize their performing movements from inside of their body, as if they are looking through their own eyes while performing the movements. For the kinesthetic imagery, the participants will be requested to perceive their body sensations of the movements without any movement. During the MI practice, the participants will be asked to (a) avoid moving or contracting muscle from their leg, and keep a relaxed position (b) keep their eyes close throughout the practice (c) keep track of the number of sequences imagined with their fingers if necessary (d) if they lose their concentration during the practice, open their eyes, relax for a few moments and then continue the practice of the task. In the tasks of forward and then backward stepping tasks, the rhythm will be trained with metronome. In the walking tasks, the participants will be asked to walk along the 8 meters walkway and back towards the starting point and repeat the walking during the prescribed duration. The participants will be trained until they are able to reproduce the tasks correctly demonstrating declarative knowledge of the sequence.

2nd to 4th week Training

Stage 1: Body Relaxation and Awareness Stage

The participants will be asked to sit on the chair and the instructions will be given. They may open or close their eyes depend on preferring. Therapist will explain about two steps of the exercise. First, contraction of particular muscle group in the body. Next, releasing the tension and notice how the muscles feel in relaxation. The participants will be asked to contract their muscles when therapist say tense your muscle or move your body part, maintain this tension when therapist say hold, release this contraction when therapist say relax. Participants will be asked to maintain this relaxation up to the end of training.

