For the control group, they will receive 25 minutes of health education. The education will be provided by the researcher using the documents. One HE topic will take 2 treatment sessions and there will be 6 topics for the whole intervention period, 4 weeks. The training schedule for health education is described.

Topic	Duration (min)	Treatment session	Content
1. Changes caused by stroke	25	1 st and 2 nd	The most common general effects of stroke Common changes with a left-brain injury Common changes with a right-brain injury Common emotional effects of stroke Factors on which improvement depends
2. Complications after stroke	25	3 rd & 4 th	Common complications of stroke Treatments for complications after stroke
3. Emotional changes after stroke	25	5 th & 6 th	The way stroke cause emotional changes Some common emotional changes after stroke The way to cope changing emotion
4. Living at home after stroke	25	7 th & 8 th	Factors to going home Changes to do at home
5. High blood pressure (HBP) and stroke	25	9 th & 10 th	What is HBP? HBP and stroke risk Persons at higher risk for HBP.

Topic	Duration (min)	Treatment session	Content
6. Preventing recurrent stroke	25	11 th & 12 th	Controllable risk factors Uncontrollable risk factors Stroke warning signs

SPCCT

SPCCT program will include 7 different workstations intended to meaningful tasks related to gait performance. To get the effect of increasing therapy, it will involve the practice of higher levels of functional activities such as standing and walking. The training package will be provided according to participant's condition in terms of muscle strength and mobility status. The practice of the tasks will be serial in order. In the training the participants will be in the pairs. The practice will be as the distributed pattern. During the rest period of one participants who will observe the performance of partner and give encouragement to do the best. Each participant will receive activity log book in which the number of repetitions of performance will be entered and it will be used as the feedback in next station.

Training schedule of SPCCT is described in the following.

SPCCT details	Duration (min)
Warm up	3
1. Stepping forward-backward onto block	4 min practice, 4 min rest, 1 min transfer (9 min)
2. Stepping sideway onto block	9
3. Heel lifts in standing to strengthen affected planter-flexor muscles	9
4. Standing with a decreased base and reach for object	9

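### The protocol claims participant blinding and a double-blind design, but participants know which add-on they receive, so expectation is not excluded as a contributor to the group difference.

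*Protocol*

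**What the plan says.** Protocol section 1.2 makes two statements about blinding. The first is "The assessor and the participants will be blinded from the study". The second, under Study Design, begins "The study design will be a randomized double blind balanced parallel-group (1:1".

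Section 1.5 describes what happens before written consent: "All participants will be explained about details of the study and the interventions". It then sets out the contrast between groups: "The experimental group will receive MI training, whereas, the control group will receive health education which both will be provided by the researcher". Both groups receive the same circuit class training, and the two add-ons are matched for duration and frequency.

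Section 1.6 describes the add-ons. For imagery, "During the training, they are not supposed to perform the activity but only imagine about the tasks". For the comparator, "For the control group, they will receive 25 minutes of health education", given by the researcher from documents on six stroke-related topics.

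Section 1.5 lists the functional gait tests as follows: "six-minute walk test will be assessed for determining walking endurance, step test will be assessed for dynamic balance, and Timed Up and Go (TUG) test". Strength by hand-held dynamometer is a secondary outcome. The SAP does not mention blinding, expectation or credibility.

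**The concern.** A participant who has been told about both interventions and then sits with eyes closed imagining steps and walking knows that this is not health education, and the reverse holds too. The protocol nevertheless tells its readers that participants were blinded.

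The label matters because several outcomes depend on how hard the participant tries. If people in one group expect more benefit and push harder at the 2-week and 4-week tests, that extra effort enters the estimated MI-versus-HE difference and cannot be separated from an effect of imagery. A larger sample would not remove it. A reader who trusts the double-blind label would rule this explanation out when the design does not.

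**Working it through.** The plan states no figure that bears on this point, so there is none to reproduce. The check is a comparison of the texts, followed by an illustration of scale.

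**Is participant blinding possible as described?**

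| Question | What the documents give |
|---|---|
| Is blinding claimed? | Yes, twice in section 1.2 |
| Are participants told what the interventions are? | Yes, before consent (1.5) |
| Can the recipient tell the add-ons apart? | Yes: imagery of four gait tasks versus education from documents (1.6) |
| How often? | 3 sessions a week × 4 weeks = 12 sessions, 25 minutes of add-on each |
| Is there sham imagery? | None described |
| Is the hypothesis concealed? | Not described |
| Is there a check of blinding or expectation? | None in either document |

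Each participant meets the distinguishing activity at up to 12 sessions. Unawareness of the activity received is not achievable under this description.

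**Does matching solve it?** The imagery add-on takes 3 + 8.5 + 2 + 8.5 + 3 = 25 minutes, the same as the education. That equalises contact time and attention. It does not equalise what people believe the add-on will do for their walking.

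**Could beliefs differ?** The imagined tasks resemble the tests. Stepping onto a block is close to the step test, and rising from a chair, walking 3 m and returning is close to the Timed Up and Go. The 8 m imagery walks have the same length as the measurement walkway in section 1.4. None of the six education topics in section 1.6 is about gait. All participants are screened for imagery ability (1.3), which may hint at the subject of the study. These features make a difference in expectation plausible; they do not prove one.

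**Which outcomes?** The six-minute walk, step test, Timed Up and Go and dynamometry need voluntary effort. The spatio-temporal variables are not itemised and the walking pace at test is not given, so only *possibly some* of them can be included. No claim is made for the spasticity rating. No scripted instruction or encouragement for the tests is described.

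**Scale, by assumption only.** Section 1.1 gives 15 + 5 = 20 and 11 + 9 = 20 participants. Take a two-sided t-test at 0.05 with 38 degrees of freedom (the SAP does not state sidedness), no true MI effect, and an expectation shift of b SD in one group.

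- Standard error of the difference at one visit = √(2/20) = 0.316 SD.
- Shift in standard errors = b / 0.316.

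| Assumed b (SD) | Shift in standard errors | Chance of p < 0.05 |
|---|---|---|
| 0 | 0 | 5.0% |
| 0.1 | 0.32 | 6.1% |
| 0.2 | 0.63 | 9.5% |
| 0.3 | 0.95 | 15.2% |

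This is a single-visit comparison of means. The SAP plans a two-way mixed repeated-measures ANOVA with a group-by-time interaction. For change from baseline to one later visit, with equal variances, the standard error is multiplied by √(2(1 − ρ)), where ρ is the within-person correlation. That factor is 1 only at ρ = 0.5, and ρ is not given. The table therefore shows how a modest shift would behave at 20 per group; it does not estimate bias in the planned test.

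**The case against.** The strongest reply is that knowing one's activity is not the same as knowing it is the favoured one, and the bias argument needs the second. Section 1.5 does not say that the hypothesis, the expected direction or the experimental label is disclosed. The consent pages were removed before review, so a neutral explanation may already be in use. This stands. A reader might infer that participants know imagery is the treatment under test; the documents do not support that. What remains is that the protocol claims blinding without qualification and describes no concealment of the hypothesis.

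Second, the comparator is a real one: same circuit training, same add-on duration and frequency, both add-ons delivered by the researcher. This also stands, and it limits attention effects. It leaves expectation open.

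Third, a reader might infer that every outcome is affected. That goes too far, because the spatio-temporal variables are not listed and their dependence on effort cannot be judged.

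Fourth, recipients of imagery or education can hardly be kept unaware of what they are doing. True, and common in rehabilitation trials. That excuses the design, not the label.

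**Conclusion.** The statements that participants are blinded and that the trial is double-blind are unsupported by the protocol's own description and should be corrected. The consequence is a limit on interpretation: the MI-versus-HE difference on the six-minute walk, step test, Timed Up and Go and dynamometry, and possibly on some spatio-temporal variables, may include a contribution from expectation.

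Its size is unknown. The 0.1 to 0.3 SD range is an assumption with no source in the documents, and the conclusion does not depend on it. It rests on two things: the add-ons are recognisable to those who receive them, and no sham or concealment of the hypothesis is described. It would be unsound to conclude that the results are biased or the trial uninterpretable. Once the blinding is described truthfully, the trial can be read as a comparison with participants aware of their intervention and an attention-matched control.

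**What to change.** 1. In section 1.2, take participants out of the blinding sentence and replace the double-blind label under Study Design with wording that names who is blinded. Both places need changing, or the contradiction survives. If participants are blinded only to the hypothesis, say so and state what they are told.
2. Use one fixed script, with identical instructions and encouragement in both groups, for all outcome tests.
3. In the explanation to participants (section 1.5), describe MI and HE neutrally as two add-ons to the same circuit training, if this is not already done.
4. State in the conclusions that the MI effect may include expectation.

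The cost is protocol wording and a short test script, with no extra staff. The trial gives up the double-blind label. Section 1.5 has the consent form approved by the institution's committee, so any change to consent wording may need re-approval. Section 1.1 reports the study population in the past tense; if enrolment is complete, items 2 and 3 come too late, but items 1 and 4 remain possible.

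The assessor half of the same sentence is a separate matter: section 1.2 has the researcher doing the assessments and section 1.5 a trained therapist. Those passages must be reconciled before the new wording can say who is blinded.

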1.3 SELECTION CRITERIA

Inclusion criteria

1. First stroke diagnosed by neurologists and has paresis on the unilateral side of the body
2. Age between 18 and 75 years
3. Poststroke duration between 3–12 months confirmed by CT report.
4. Patients with middle cerebral artery (MCA) involvement
5. Ability to walk at least 10 meters with or without using assistance (walking aid and/or orthosis).
6. Functional Ambulation Category (FAC) ≥ 3 from the total of 5 score
7. Good cognition assessing by the Mini Mental State Examination (MMSE) ≥ 24 from the total of 30 score
8. National Institutes of Health Stroke Scale (NIHSS) < 14 from the total of 42 score
9. Proper MI ability assessing by the Kinesthetic and Visual Imagery Questionnaire (KVIQ–10) ≥ 3 from the total of 5 score

Exclusion criteria

1. Unstable cardiopulmonary problems (resting heart rate > 120 bpm, resting systolic blood pressure > 180 mmHg and resting diastolic blood pressure > 100 mmHg)
2. Other neurological conditions such as Parkinson's disease, Alzheimer's disease, or epilepsy
3. Orthopedic and rheumatologic disorders with weight bearing pain
4. Unable to communicate or unable to follow commands
5. Serious cardiac conditions such as hospitalization for heart disease within 3 months, active angina, serious cardiac arrhythmias, hypertrophic cardiomyopathy, severe aortic stenosis
6. Patients with unilateral spatial neglect
7. Patients with ataxic movement
8. Patients under medications with muscle relaxing effect

Termination Criteria

1. Borg scale for Rating Perceived Exertion (RPE) > 13 from the total of 20 score
2. Drop in systolic blood pressure 10 mmHg (persistently below baseline), despite an increase in workload, when accompanied by any other evidence of ischemia
3. Central nervous system symptoms such as dizziness, or near syncope
4. Signs of poor perfusion such as cyanosis or pallor
5. Severe adverse event, this means falls or incidents leading to injury requiring hospital or general practitioner visit
6. Another episode of stroke

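### Blood pressure and pulse are read for safety, but no written stop acts on a high value, and isolated cardiac events are not named as stops

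*Protocol*

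**What the plan says.** **Monitoring (protocol 1.5).** "For the safety, the therapist will measure blood pressure, pulse rate and fatigue level in the assessments, just before the training, and rest period". Assessments take place at baseline, 2 weeks and 4 weeks, and they include a six-minute walk test.

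**Entry (protocol 1.3, exclusion criteria).** Item 1 excludes "Unstable cardiopulmonary problems (resting heart rate > 120 bpm, resting systolic blood pressure > 180 mmHg and resting diastolic blood pressure > 100 mmHg". Item 5 excludes "Serious cardiac conditions such as hospitalization for heart disease within 3 months, active angina, serious cardiac arrhythmias", with further cardiac diagnoses.

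**Stopping (protocol 1.3, termination criteria).** There are six items. Item 1 is perceived exertion above 13 on the Borg scale. Item 2 is "Drop in systolic blood pressure 10 mmHg (persistently below baseline), despite an increase in workload, when accompanied by any other evidence of ischemia". Items 3 and 4 are neurological symptoms and visible poor perfusion. Item 5 is "Severe adverse event, this means falls or incidents leading to injury requiring hospital or general practitioner visit". Item 6 is "Another episode of stroke". The section does not say whether termination ends the session or ends the patient's participation.

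**Elsewhere.** In section 1.6 pulse is used only to check engagement in motor imagery. The SAP contains no safety rule.

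**The concern.** A safety reading protects the participant only if the plan says what to do when it is abnormal. Of the three things measured for safety, fatigue has an upper limit, while blood pressure and pulse have none. The protocol does hold numeric limits for both, but as conditions of entry, and nothing says that they are applied again before a session or an assessment.

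Take a patient who enters at 150/90 and arrives for a later session at 200/110 without symptoms. No written criterion is met, so on the text that patient may go on to progressive stepping, fast walking or the six-minute walk. Similarly, a patient who develops angina or a serious arrhythmia, or is admitted for heart disease, during the four weeks would be ineligible to enroll but meets no named reason to stop.

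What is at stake is participant safety, and consistency between therapists and hospitals in responding to the same reading.

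**Working it through.** The plan states no figure to reproduce. The check sets the stop list against the safety readings and the entry bars, then counts what a rule would cover and cost.

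**1. The six termination criteria**

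| Criterion | Acts on high blood pressure? | Acts on a pulse value? | Names angina, arrhythmia or cardiac admission? |
|---|---|---|---|
| 1. Exertion above 13 | No | No | No |
| 2. Systolic fall with other ischemia | No, a fall only | No | No; angina could serve as the ischemia, but only with the fall |
| 3. Neurological symptoms | No | No | No |
| 4. Poor perfusion | No | No | No |
| 5. Severe adverse event | No | No | No; defined through falls and injury |
| 6. Recurrent stroke | No | No | No |

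Result: 0 of 6 act on a high blood pressure, 0 of 6 on a pulse value, and 0 of the 3 cardiac events is named.

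**2. Readings that a rule would cover.** Inputs: 40 participants, 3 sessions a week for 4 weeks (protocol summary), 3 assessments (section 1.5). I assume one reading just before each session.

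- Sessions per participant: 3 × 4 = 12.
- Pre-training readings: 40 × 12 = 480.
- Assessment visits: 40 × 3 = 120.

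**3. Cost of a pre-session hold.** The documents give no rate of high readings, so I assume that a fraction p of them, 1% to 5%, exceeds a limit. Participants train in pairs, so a deferral can also disrupt a partner whose own reading is normal. With partners independent, the number of sessions affected is 480p + 480p(1 − p).

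- p = 0.01: 480 × 0.01 = 4.8 deferred; 480 × 0.01 × 0.99 = 4.75 partner sessions; total 9.55, and 9.55 / 480 = 1.99%.
- p = 0.05: 480 × 0.05 = 24 deferred; 480 × 0.05 × 0.95 = 22.8 partner sessions; total 46.8, and 46.8 / 480 = 9.75%.
- Per participant: 9.55 / 40 = 0.24 to 46.8 / 40 = 1.17 of 12 sessions.
- Assessments, at the same assumed rate: 120 × 0.01 = 1.2 to 120 × 0.05 = 6 deferred.

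**4. Cost of a cardiac stop.** At worst one participant loses all 12 sessions: 12 / 480 = 2.5% of sessions, and 1 of 20 in an arm (5%), per event.

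**The case against.** The strongest reply is that the patients are already protected. Exertion is capped, dizziness, near syncope, cyanosis and pallor each stop the patient, 4 minutes of rest follow 4 minutes of practice, and the circuit is run by a "physiotherapist who have 5 years experienced in neurological condition". Most cardiac events would show through one of those routes. A patient in hospital is not training in any case, and a generous reader might place a cardiac admission under item 5. All of this reduces the gap. It does not close it: an asymptomatic high reading triggers none of these stops, item 5 goes on to define its own term through falls and injury, and nothing governs return after a cardiac admission.

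Three stronger readings are tempting, and the documents do not support them.

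- **That exclusion 1 admits anyone who does not exceed all three limits at once.** The word 'and' allows this literally, but the text is a bracketed list of problems, each with its own limit, so 'or' is probably meant. This is a clarification of wording.
- **That every rest-period reading belongs in the size of the problem.** Seven rests in 480 sessions would give up to 3,360 readings, but section 1.5 does not say that every rest is measured. The entry limits are resting values, and the documents give no exertional limit to apply in their place.
- **That the plan ignores serious events, or that the result is biased.** Recurrent stroke is already a stop under item 6, and no estimate or comparison depends on this point.

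It is also fair to say that using entry limits as session limits is a clinical judgement, and that deferrals work against the aim of matched frequency in section 1.5. Both points stand, as limits on the fix.

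**Conclusion.** The concern holds as a patient-safety gap that should be corrected. The plan takes safety readings of blood pressure and pulse without saying what follows a high one, and it does not name as stops three cardiac events that it treats as too serious for entry. What remains after the existing safeguards is the asymptomatic high reading and the isolated cardiac event.

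The part that can be closed from the protocol's own limits covers 480 pre-training readings and 120 assessment visits. These are counts of readings, not of risk: the documents give no rate of high readings or of cardiac events. Confidence is high that the gap exists, and lower that the entry values are the best session limits. Rest-period readings remain under termination items 1 to 4.

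**What to change.** 1. **Hold rule.** If resting heart rate exceeds 120 bpm, systolic pressure 180 mmHg or diastolic pressure 100 mmHg (any one) just before a training session or an assessment, defer that session or assessment. State that this hold does not end participation. Word exclusion 1 with 'or', so that the limits read the same way at entry.
2. **Cardiac stops.** Add new angina, serious arrhythmia and cardiac admission as criteria that end participation. Count these, and recurrent stroke, as severe adverse events. An ordinary medical visit should not be a stop.
3. **Make-up sessions.** Make up deferred sessions within the 4 weeks where possible.

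Blood pressure and pulse are already measured, so no new measurement is needed. The price is some deferred sessions, since "In the training the participants will be in the pairs": about 2% to 10% of the 480 sessions on the assumed 1% to 5% rate. A deferred assessment may also fall away from its planned week. Each participant stopped for a cardiac event loses the remaining sessions, and perhaps later outcome values, for which the SAP gives no rule. Writing 'or' may exclude some patients whom a literal 'and' would admit; the documents do not allow a count.
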